Gradable laboratory values will be evaluated and assigned toxicity grades according to the NCI CTCAE v5.0. Clinically significant post-baseline laboratory values will be reported as AEs. When possible, a diagnosis should be recorded as an AE, rather than the symptoms or isolated laboratory abnormalities related to the diagnosis.

Shift tables will be presented to indicate the number and percentage of patients with directional shifts in CTCAE toxicity grades relative to the baseline, when assessing the worst change (i.e., minimum and/or maximum) in the value of each laboratory test during the treatment period. With regard to laboratory parameters without CTCAE toxicity grades (e.g., serum immunoglobulin), similar shift tables will be constructed per normal range to index the shifts above or below the normal range relative to that of the baseline with the categories of < LLN, WNL and > ULN. WNL and normal will be used when appropriate for urinalysis parameters.

Summary statistics will be provided for gradable parameters with either both directions (e.g., hypocalcemia for the low value of calcium and hypercalcemia for the high value of calcium) or only one of the directions as long as the grading criteria are available per the CTCAE. Subjects will be counted only once for each criterion/direction, but the same subject can be counted for both criteria if the subject has laboratory values that meet each criterion. Subjects who meet the criteria of Grade 1 or higher for the high direction will be classified under Grade 0 for the summarization of the low direction if the CTCAE term for low direction

Regeneron Pharmaceuticals Inc. / Protocol: CMP-001-011 IQVIA Biotech (Confidential) Project # SZA58924

exists, and vice versa. Change from baseline will be calculated for each parameter of interest when both the baseline and post-baseline values are non-missing.

Additionally, a summary of Hy's Law criteria will be included to indicate if there is any subject potentially meeting Hy's Law criteria during the study for Liver Function Tests (LFTs). The components of the criteria are as follows:

- ALT or AST >= 3xULN (i.e., upper limit of normal)
- Total Bilirubin >= 2xULN
- ALP < 2xULN

Subjects potentially meeting Hy's Law Criteria is defined as those whose ALT or $AST \ge 3xULN$, Total Bilirubin $\ge 2xULN$ and ALP < 2xULN at the same visit.

2. Changes in Laboratory Values from Baseline

Hematology and serum chemistry will be summarized in a descriptive manner for the following values that will be derived per unique subject and parameter:

[figure not shown]
- Baseline value
- Minimum post-baseline value and corresponding change from baseline
- Maximum post-baseline value and corresponding change from baseline
- Last post-baseline value and corresponding change from baseline

The baseline value will be determined using the convention described in Section VI.B. In addition, incidence of the most extreme post-baseline laboratory abnormality from the treatment-emergent period will be summarized for the corresponding parameter. A treatment-emergent laboratory abnormality is defined as a laboratory value whose grade is at least one grade higher than the baseline grade.

By-subject data listings of all central laboratory data will be generated, and all values outside the normal range will be flagged as High or Low. Listings of all clinically significant post-baseline laboratory values from local and central laboratory assessments will be presented in the data listings.

Table 3: Clinical Laboratory Assessments

Hematology	Serum Chemistry	Urinalysis	Other Laboratory
			Tests

Regeneron Pharmaceuticals Inc. / Protocol: CMP-001-011 IQVIA Biotech (Confidential) Project # SZA58924

Red blood cells (RBCs)	Alanine	Blood	Coagulation:
White blood cells	aminotransferase	Glucose	Partial thromboplastin
(WBCs)	Albumin	Nitrites	time
Differential WBC count	Alkaline phosphatase	pH	Prothrombin time
Total leukocyte count,	Amylase	Protein	International
including differential	Aspartate		normalized ratio
Hemoglobin	aminotransferase	Specific gravity	
Hematocrit	Bilirubin	WBCs	Thyroid Function
Platelets	Blood urea nitrogen or		Studies:
	serum urea	Microscopic battery:	TSH, T3, free T4 (at
	Calcium	RBCs, WBCs,	Screening)
	Chloride	epithelial cells, casts (only if significant	TSH, with reflexive
	Creatinine	positive findings on	T3 and free T4 if TSH
	Glucose	urinalysis)	is abnormal (on treatment)
	Lactate dehydrogenase		ireatificiti)
	Lipase		Autoimmune
	Phosphorous		laboratory panel:
	Potassium		Anti-doubled stranded
	Sodium		DNA, antinuclear
	Total protein		antibody,
	Total protein		antineutrophil
			cytoplasmic antibody,
			rheumatoid factor, and
			antibodies to ribonucleoprotein
			HIV
			Hepatitis B and C
A11 '	DDC 111 1 11 T	2	nepaulis B and C

Abbreviations: RBC = red blood cell; T3 = triiodothyronine; T4 = thyroxine; TSH = thyroid stimulating hormone; WBC = white blood cell.

Note: Refer to the Laboratory Manual for additional information.

E. Vital Signs

The following vital signs were measured at screening and periodic time points (including end of treatment) following the initiation of study treatment:

- Systolic and diastolic blood pressures (mmHg)
- Respiratory Rate (breaths/min)
- Pulse Rate (beats/min)
- Body temperature (Celsius)

Each of these vital signs will be summarized in a descriptive manner for the following values that will be derived per unique subject:

Regeneron Pharmaceuticals Inc. / Protocol: CMP-001-011 IQVIA Biotech (Confidential) Project # SZA58924

- Baseline value
- Minimum post-baseline value and corresponding change from baseline
- Maximum post-baseline value and corresponding change from baseline
- Last post-baseline value and corresponding change from baseline

The baseline value will be determined using the convention described in Section VI.B. Vital signs will be summarized by treatment arm and overall using descriptive statistics and presented for each time point from baseline to all subsequent post-baseline assessments, including the actual values and change from baseline, for the Safety Analysis Set. Clinically significant post-baseline vital sign findings will be reported as AEs. A by-subject data listing of all vital sign data will be generated.

F. Physical Examination

Detailed information on the physical examinations (height, weight, and BMI) will be listed by subject. Clinically significant post-baseline physical examination findings will be reported as AEs.

G. Prior and Concomitant Medications

All medications administered to the subject from 30 days prior to the first dose of the study drug (W1D1) until 100 days after the last dose of the study treatment (CMP-001 and nivolumab) or until the initiation of an alternative new anti-cancer treatment, whichever occurs first, will be recorded in the EDC. Treatment medications for AEs related to study treatment that occur more than 100 days after the last dose date of the study treatment will also be collected. In addition, at each LTSFU contact, an inquiry will be made regarding the start of any new cancer treatments since the date of the last contact.

Documentation for each medication will include the generic name of the medication, total daily dose, route of administration, date of administration, and indication for use. Combination drugs must be listed separately by each component product and dose. Prior cancer treatment will be recorded separately.

Prior medications. Prior medications are defined as those taken within 30 days prior to the first dose of the study treatment and discontinued before the first dose date of the study treatment.

Concomitant medications. Concomitant medications are defined as medications which are taken at any time prior to 100 days after the last dose of the study treatment (both CMP-001 and nivolumab) or until the initiation of an alternative new anti-cancer treatment, whichever is earlier, and stopped at any time on or after

Regeneron Pharmaceuticals Inc. / Protocol: CMP-001-011 IOVIA Biotech (Confidential) Project # SZA58924

the first dose date of the study drug. Medications with missing or partially missing start or end dates will be handled according to the conventions described in Section VI.C. If it cannot be determined whether a medication is a prior medication due to partial medication start or end dates, the medication will be considered concomitant. Treatment medications for study-related AEs that occur more than 100 days after the last dose of study drug will be collected.

Medications will be coded using the World Health Organization (WHO) drug dictionary version B3 Global September 2020 (or later) and might be up-versioned by the end of the study. Concomitant medications will be summarized according to the Anatomical Therapeutic Chemical (ATC) class II and preferred term for Safety Analysis Set. The number and percentage of subjects taking concomitant medications will be summarized for each treatment arm in the Safety Analysis Set. Subjects will be counted only once for a given concomitant medication for each ATC class and preferred term in the summary tables. Prior medications will be summarized using the ITT Analysis Set.

Concomitant medications will be presented in a by-subject data listing. The listing will contain the information on both the prior and concomitant medications with an indication on whether the medication is prior or concomitant. The listing will display entries from the Concomitant Medications form, ordered within subject by the Start Date of Medication and listed terms alphabetically.

H. Prior and Concomitant Procedures

All procedures administered to the subject within 30 days prior to the first dose of the study drug (W1D1) until 100 days after the last dose of the study drug (CMP-001 and nivolumab) or until the initiation of an alternative new anti-cancer treatment, whichever occurs first, will be recorded in the EDC.

Prior procedures. Prior procedures are defined as procedures performed within 30 days prior to the first dose of the study drug and discontinued before the first dose date of the study drug.

Concomitant medications. Concomitant procedures are defined as procedures which are performed at any time prior to 100 days after the last dose of the study drug (both CMP-001 and nivolumab) or until the initiation of an alternative new anti-cancer treatment, whichever is earlier, and stopped at any time on or after the first dose date of the study drug.

Concomitant procedures will be presented in a by-subject data listing. The listing will contain the information on both the prior and concomitant procedures with an indication on whether the procedure is prior or concomitant. The listing will

Regeneron Pharmaceuticals Inc. / Protocol: CMP-001-011 IQVIA Biotech (Confidential) Project # SZA58924

display entries from the Concomitant Procedures form, ordered within subject by the Start Date of Procedure. The listing will also display the recorded terms from the eCRF, adjacent to which, the system organ class and the preferred term will be shown.

I. Electrocardiograms (ECGs)

The 12-lead ECGs were performed at Screening, before the W1D1, W3D1, and W7D1 CMP-001 injections and at end of treatment visit of the study. The following ECG parameters and clinical findings were collected:

- Heart rate (beats/min)
- PR interval (msec)
- QRS interval (msec)
- QT interval (msec)
- QTcF interval (msec)

The mean of the replicate ECG measurements will be calculated and used for the analysis whenever replicates are reported for a subject at a time point. Summaries of actual values and changes from baseline will be presented for each assessment visit. Additionally, each ECG parameter will be summarized in a descriptive manner by treatment arm in the Safety Analysis Set for the following values that are derived per unique subject and ECG parameter:

- Baseline value
- Minimum post-baseline value and corresponding change from baseline
- Maximum post-baseline value and corresponding change from baseline
- Last post-baseline value and corresponding change from baseline

Overall interpretation of ECG parameters (i.e., "Normal", "Abnormal, Not Clinically Significant" and "Abnormal, Clinically Significant") at baseline and any applicable post-baseline visit and time point will be summarized categorically with the number and percentage of patients tabulated. Clinically significant post-baseline ECG findings will be reported as AEs.

Categorical analyses of QTcF interval across time points will be performed to display the number and percentage of subjects in a shift from baseline manner with the following thresholds (exclusive categories) to indicate the status of the worst post-baseline value of QTcF (i.e., basically, the maximum post-baseline value) and the status of the last post-baseline value:

- <= 450 msec
- 450 to <= 480 msec
- 480 to <= 500 msec

Regeneron Pharmaceuticals Inc. / Protocol: CMP-001-011 IQVIA Biotech (Confidential) Project # SZA58924

• > 500 msec

Moreover, the number and percentage of subjects with an increase in QTcF interval from baseline will also be tabulated with the following categories (inclusive levels) to display the status of the maximum post-baseline value of QTcF and the status of the last post-baseline value:

- > 30 msec
- \bullet > 60 msec

Detailed information on all ECG data will be depicted by means of a by-subject data listing.

X. Pharmacodynamic Analyses

Concentrations of CXCL10 and other biomarkers will be summarized using descriptive statistics for all time points for the Pharmacodynamic Analysis Set, provided that there are data available for the analysis set to be defined and analysis to be performed.

XI. Exploratory Tumor Biopsy Analyses

Tumor biopsy obtained at Baseline and specified time points during the study may be analyzed for protein, RNA, DNA, or other biomarkers related to TLR9, immune checkpoints, and potential markers of resistance or response to immunotherapy for the Pharmacodynamic Analysis Set, provided that there are data available for the analysis set to be defined and analysis to be performed.

Regeneron Pharmaceuticals Inc. / Protocol: CMP-001-011 IQVIA Biotech (Confidential) Project # SZA58924

XII. References

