Baseline is defined as the last non-missing observation on or prior to the first administration of study drugs (CMP-001 or Nivolumab), including assessments on Day 1 that are pre-dose. Study Day 1 will be designated as the first day when a subject receives either study drug (i.e., Week 1 Day 1).

Regeneron Pharmaceuticals Inc. / Protocol: CMP-001-011 IQVIA Biotech (Confidential) Project # SZA58924

C. Missing Data

Unless stated otherwise, missing data will not be replaced with imputed values. When relevant, sections below will address how missing data will be handled for the particular analyses.

Missing or Partial Death Dates

A death date missing the month and day will be imputed as Jan 1st of the year or the day after the date of last known alive, whichever comes later.

A death date missing the day will be imputed as the 1st of the month or the day after the date of last contact, whichever comes later.

Missing Dates in Adverse Events/ Concomitant Medications

Every effort will be made to avoid missing/partial dates in on-study data including AE and medication start and stop dates.

Start dates of AEs/ Concomitant medications will be imputed as follows:

• Completely missing start date will not be imputed.

Start date missing both the month and day will be imputed as:

- The date of the first dose if the year of the start date is the same as the date of first dose.
- Otherwise, Jan 1st of the year of the start date will be used.

Start date missing the day will be imputed as:

- The date of first dose if the year and month of the start date are the same as the date of first dose.
- Otherwise, the 1st day of the month of the start date will be used.

Stop dates of AEs/ Concomitant Medications will be imputed as follows:

- Completely missing stop date will not be imputed.
- Stop date missing both the month and day will be imputed as Dec 31st of the year of stop date.
- Stop date missing the day will be imputed as the last date of the month of the stop date.

After imputation, the imputed date will be compared against the date of death, if available. If the planned imputed date is later than the date of death, the date of death will be used as the imputed date instead.

Regeneron Pharmaceuticals Inc. / Protocol: CMP-001-011 IQVIA Biotech (Confidential) Project # SZA58924

Missing Dates in Prior Medications

Start or Stop dates of Prior Medications will be imputed as follows:

- Completely missing start or stop date will not be imputed.

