- Start or stop date with missing both the month and day will not be imputed.
- Start date missing the day will be imputed as the 1st day of the month of the start date.
- Stop date missing the day will be imputed as the last date of the month of the stop date or the study first dose date, whichever comes earlier.

D. Multiple Study Centers

No adjustment for study center is planned. Data from all investigational sites will be pooled in the analyses.

E. Covariate Adjustment in Primary Analysis

No covariate adjustments are planned.

F. Sample Size Reassessment

Not applicable.

G. Ad-hoc Analysis

There will be an ad-hoc analysis planned with the trigger event being two disease assessments after the enrollment of the last subject. The ad-hoc analysis of the endpoints will follow the efficacy analysis methods described in Section 0 below as well as the safety analysis methods detailed in Section IX below for the exploratory Phase 2 study.

The following unblinded subject information, efficacy-related and safety-related data displays will be produced for the purpose of the ad-hoc analysis. Unless stated otherwise, these displays are summary tables that summarize data by treatment group:

- Subject information
 - Demographics
 - Baseline characteristics
 - Disposition

Regeneron Pharmaceuticals Inc. / Protocol: CMP-001-011 IQVIA Biotech (Confidential) Project # SZA58924

- Medical history
- Cancer history
- ECOG

Efficacy

- o ORR, DOR, TTR, PFS per RECIST v1.1 by BICR and Investigator
- o OS
- Selected subgroup analysis

Safety

- Study drug exposure: CMP-001 and nivolumab
- Prior and concomitant medications
- Prior and concomitant procedures
- o All TEAEs (SAE, AESI)
- Summary of clinical laboratory results
- Summary of ECG results

H. Test Sizes

Given Sponsor's decision to terminate the study enrollment early, any tested hypotheses will be exploratory in essence and tested against 2-sided alternatives, using procedures that provide an expected probability of Type I error (α) of 0.05.

I. Multiplicity

Provided that the study enrollment was terminated early per Sponsor's consideration and the trial has been changed to an exploratory Phase 2 study, the previous sequential gatekeeping strategy is not applicable here anymore, and there will be no control for multiplicity applied. Thus, any tests performed will simply be exploratory and interpreted as such.

J. Analysis Sets

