All events of RECIST v1.1 disease progression or death will be counted regardless of whether the event occurs while the subject is on study treatment or previously discontinued the study treatment. Subjects who do not experience disease progression or death as of the analysis cutoff date or final database lock will be censored at the date of the last adequate tumor assessment. Date of censoring for these subjects will be based on the last tumor assessment prior to missing the assessments. Censoring rules are summarized in Table 1. If a subject meets the criteria for more than one censoring rule, PFS will be censored at the earliest censoring date. Unless specified otherwise, the analysis methods described for DOR will be used for PFS. Additionally, the analysis of PFS based on RECIST v1.1 as determined by Investigator assessment will also be performed.

Overall Survival (OS). Overall survival will be calculated as the time from the date of randomization to the date of death due to any cause. Subjects who are alive or lost to follow-up as of the analysis cutoff date will be censored at the time of the last study contact date (i.e., date of last known alive). The last contact date will be derived as detailed in Table 2.

Based on these considerations, OS will be calculated as follows: OS (months) = (Death or Censoring Date – Date of Randomization + 1) / 30.4375

Regeneron Pharmaceuticals Inc. / Protocol: CMP-001-011 IQVIA Biotech (Confidential) Project # SZA58924

OS will be analyzed using the Kaplan-Meier method by treatment arm of the ITT Analysis Set. A Kaplan-Meier plot of OS will be generated for each treatment arm. The analysis methods described for DOR will be used for OS, unless specified otherwise.

Disease Control Rate (DCR). The confirmed disease control rate is defined as the proportion of subjects in each treatment arm in the analysis set who have a confirmed best response of CR, PR, or stable disease (SD) lasting at least 4 months. Per RECIST v1.1, CR or PR must be confirmed by a confirmatory assessment performed at least 4 weeks after the initial response. In the case of SD, measurements must have met the SD criteria at least once after study entry at a minimum interval of 6 weeks. Overall response assessment evaluated after subsequent new anti-cancer therapy will not be considered for DCR calculation.

DCR will be analyzed in a similar manner as ORR. Specifically, DCR and the associated 95% Clopper-Pearson CIs will be summarized.

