Last contact date/last date patient known to be alive from Long-Term Follow-Up eCRF 100-Day Follow-Up eCRF	Use if patient status is reported to be alive. Do not use if patient status is not reported unknown
End of study	Not lost to follow up
Start/end dates from drug administration record	Non-missing dose. Doses of 0 are allowed
Dosing prophylaxis eCRF	Prophylaxis given marked as yes
End of treatment date(s) from the End of Treatment eCRFs	No condition
Tumor assessment (RECIST v1.1 or iRECIST) date	Evaluation is marked as done
Laboratory/PK collection dates	Sample collection marked as done
Vital signs date	At least 1 non-missing parameter value
Physical examination	Evaluation performed marked as yes
12-Lead ECG	Evaluation performed marked as yes
ECOG performance status date	Non-missing ECOG performance status
Start/end dates of adverse events	Non-missing verbatim term
Start/end dates of concomitant medications and procedures	Non-missing verbatim term

B. Primary Efficacy Analysis

Primary Efficacy Endpoint. The primary efficacy endpoint for the exploratory Phase 2 study is the confirmed ORR based on RECIST v1.1 as determined by BICR. ORR and the 95% exact CIs will be calculated using the Clopper-Pearson method for each of the 2 treatment arms in the ITT Analysis Set.

Regeneron Pharmaceuticals Inc. / Protocol: CMP-001-011 IQVIA Biotech (Confidential) Project # SZA58924

Given Sponsor's decision to terminate the study enrollment early, the previous sample size calculated to achieve the power and effect size desired at the confidence level specified will not be reached. Hence, the analysis will simply be exploratory and interpreted as such.

C. Secondary Efficacy Analyses

The secondary efficacy endpoints include DOR, PFS, OS, DCR, treatment effect in non-injected target lesions based on the RECIST v1.1 by Investigator assessment, iORR, iDOR, and iPFS. Post-progression disease assessments of tumor response based on iRECIST evaluated by Investigator assessment will be summarized in a similar way to the RECIST v1.1 assessment, and will include the calculation of iORR, iDOR, and iPFS by treatment arm using the ITT Analysis Set as described in the previous sections.

iORR: As assessed by Investigator assessment according to iRECIST for the ITT Analysis Set in each of the treatment arm, iORR will be summarized and analyzed in a similar fashion to that of the ORR per RECIST v1.1.

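### A finished screening AE with a partial start date can be counted as a TEAE, and the SAP does not keep imputed stop dates out of the last-known-alive date for OS

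*SAP*

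**What the plan says.** SAP VI.C gives these rules for AE and concomitant medication dates:

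- Start, month and day missing: "The date of the first dose if the year of the start date is the same as the date of first dose"; otherwise 1 January of the recorded year.
- Start, day missing: "The date of first dose if the year and month of the start date are the same as the date of first dose"; otherwise the first of the recorded month.
- Stop, month and day missing: "Stop date missing both the month and day will be imputed as Dec 31st of the year of stop date".
- Stop, day missing: "Stop date missing the day will be imputed as the last date of the month of the stop date".
- One check afterwards: "If the planned imputed date is later than the date of death, the date of death will be used as the imputed date instead".

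No rule compares an imputed date with the other date of the same record, with last contact or with the data cutoff. For prior medications the same section does set a bound; a stop date without a day becomes "the last date of the month of the stop date or the study first dose date, whichever comes earlier".

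SAP IX.B.1 defines a TEAE by onset or worsening from first dose onward and treats cases that cannot be settled as treatment-emergent. An AE between consent and first dose is pre-treatment. Protocol 7.4.1 has all AEs from consent entered on the eCRF.

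For OS, the text of SAP VIII.A censors subjects who are alive or lost to follow-up at the last contact date and adds: "The last contact date will be derived as detailed in Table 2". Among the sources in Table 2 is "Start/end dates of adverse events", with a similar row for medications and procedures. The only condition in both rows is that a verbatim term is present. The OS rows of the censoring rules, however, use the last-known-alive date only for subjects lost to follow-up. The others are censored at study completion, data cutoff or study discontinuation.

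A partial death date in VI.C is set no earlier than the day after last known alive (month and day missing) or last contact (day missing).

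**The concern.** There are two separate gaps.

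**TEAE classification.** The start-date rule can override a recorded fact. If the stop date is complete and falls before dosing, the event cannot have begun on or after first dose. The rule still gives it the first-dose date, so a pre-treatment event enters the TEAE tables with a start later than its stop.

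**OS censoring.** Most other rows of Table 2 ask for some evidence of contact: an assessment marked as done, a sample collected, a status reported as alive. The AE, medication and procedure rows ask only for a term. AE and medication stop dates are imputed to the latest day compatible with what was recorded, and nothing says that such dates stay out of Table 2. The check against death gives no protection here, because a subject censored for OS has no death date. If imputed dates are admitted, a lost subject is credited with survival that nobody observed and may stay in the risk set at the 6- or 12-month reading.

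**Working it through.** The documents state no figure to reproduce. The check applies the rules literally to assumed dates.

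**Inputs.** Imputation rules from SAP VI.C; TEAE definition from IX.B.1; OS formula from VIII.A, (end date − randomization date + 1) / 30.4375; arm sizes 9 (A) and 11 (B), all 20 treated, from II.C.

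**TEAE example (assumed dates).** First dose 20 June 2022; AE stop recorded as 15 June 2022; AE start recorded as June 2022, or only as 2022.

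- Imputed start in either case: 20 June 2022, 5 days after the event ended.
- The imputed start falls on the first-dose date and has no clock time, so the default in IX.B.1 also points to treatment-emergent.
- With the start recorded as May 2022, the imputed start is 1 May 2022 and the event stays pre-treatment. The fault therefore needs a start in the first-dose month with the day missing, or in the first-dose year with month and day missing.
- Size: 1/9 = 11.1 points in Arm A and 1/11 = 9.1 points in Arm B. Subjects count once per system organ class or preferred term, so the shift is zero if the subject already has a TEAE at that level.

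**Largest shift of a stop date.**

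- Day missing: from the 1st to the 31st, 30 days; 30 / 30.4375 = 0.99 month.
- Month and day missing: from 1 January to 31 December, 364 days (365 in a leap year); 364 / 30.4375 = 11.96 and 365 / 30.4375 = 11.99 months.

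**OS example (assumed dates).** Randomized 1 June 2022; last real contact 15 March 2023, then lost to follow-up; one AE stop recorded only as 2023.

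- From real contact: 288 / 30.4375 = 9.46 months.
- From the imputed stop of 31 December 2023: 579 / 30.4375 = 19.02 months, past the 12-month reading.

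**Effect on the curve.** Months per subject are not points on the OS estimate. If one subject is wrongly kept in Arm A's full risk set at a single death, the Kaplan-Meier step changes from 1 − 1/8 = 87.5% to 1 − 1/9 = 88.9%, or 1.4 points. The change grows as the risk set shrinks: with 4 against 5 at risk it is 75% against 80%.

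**Death dates.** Suppose death and an AE stop are both recorded only as 2022. If the AE date is imputed first and admitted, last known alive is 31 December 2022 and death becomes 1 January 2023, outside the recorded year. The check against death cannot prevent this, because it needs the death date first. The SAP states no order.

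**The case against.** On OS, the SAP nowhere says that imputed dates feed Table 2. VI.C begins by ruling out imputation unless otherwise stated, the imputation rules stand under an AE and medication heading, and Table 2 lists source data, which can be read as dates as recorded. Harm also needs several conditions together: a partial stop date whose imputed value is later than every other source and, under the OS rows, a subject lost to follow-up. Protocol 8.3 asks for onset and resolution dates for all AEs, and VI.C promises efforts to avoid partial dates. All of this stands. It makes the OS effect a possibility left open, not an instruction.

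On TEAEs, defaulting to treatment-emergent is conservative, the pre-treatment definition gives a basis for correct classification, and a start after its own stop would probably be queried. But the default is for cases that cannot be settled, and a complete stop date before dosing settles the case. The rule as written gives the wrong answer and leaves correction to chance.

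Three stronger readings are tempting and are not supported:

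- That the SAP disregards known dates altogether. It uses the first-dose date and checks against death.
- That serious biopsy complications would enter the TEAE tables. Protocol 8.3 requires date and clock time of onset for SAEs, and SAP IX.B provides for reconciling the eCRF with the SAE forms.
- That OS is inflated generally. Under the OS rows, only subjects lost to follow-up could be affected.

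**Conclusion.** The TEAE point holds as a stated rule that gives a wrong result when a partial start shares the month or year of first dose and a complete stop date precedes dosing. One such subject moves a rate by at most 11.1 points (Arm A) or 9.1 points (Arm B).

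The OS point holds conditionally. If imputed dates are admitted to Table 2, censoring can be later than any observed contact by at most 30 days or about 12 months. It reaches lost-to-follow-up subjects under the OS rows, or all subjects alive under the VIII.A text. An imputed death date can also move later.

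These are ceilings. The documents do not give the number of partial dates, the analysis is descriptive and exploratory in 20 subjects, OS is secondary, and the primary endpoint (ORR) is untouched. The expected effect is modest, but in arms of 9 and 11 a single record can show, and the repair costs almost nothing.

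**What to change.** 1. VI.C: an imputed AE start date may not be later than a complete stop date, and an AE with a complete stop date before first dose is pre-treatment.
2. Table 2: use only complete, non-imputed dates on or before the data cutoff.
3. VI.C: cap imputed stop dates at the earliest of death, last contact (derived from complete dates only) and data cutoff. Deriving last contact this way also removes the circularity with imputed death dates.
4. VIII.A: reconcile the OS censoring text with the OS rows of the censoring rules, so that it is clear which subjects are censored at the last-known-alive date.

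The cost is a few SAP sentences and minor programming. No endpoint, data collection or clinical procedure changes.
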